#### 7.1.2 Stenciling

Stencils are used to trace wound areas at each visit.

1. Place the stencil directly over the wound area
2. Trace all wounds within the 50 cm^2 area
3. After the tracing, place the stencil dirty-side down on a flat, disposal surface
4. Use a clean, pre-labeled stencil to re-trace the wounds
5. Dispose of the dirty stencil
6. Make a photocopy of the clean stencil and place the photocopy in the study file
7. Place the clean stencil inside of an envelope in the study file

### 7.2 Biopsy Evaluation

There are 2 evaluations that require a tissue sample on this study: COL7 analysis by IF and AF analysis by IEM.

Throughout the study, the collection of biopsies is optional, and performed at the discretion of the Investigator and Sponsor. If a biopsy is not collected it will not be considered a protocol deviation. The biopsy schedule is outlined in **Table 2 - Schedule of Events**.

IF biopsies are processed at Stanford per Stanford standard operating procedures.

IEM biopsies are to be collected on Monday or Tuesday and shipped to Shriners Hospital to the address below for overnight or same-day delivery. Collection on Thursday or Friday should be avoided.

[name]  
Assistant Investigator  
Micro-Imaging Center

Shriners Hospital for Children  
[name]  
[name]

### **7.3 Investigator's Global Assessment Score**

Areas administered topical KB103 and placebo will be clinically evaluated at baseline and at Days 15, 30, 45, 60, 90, and unscheduled visits with an IGA score of: 1) complete closure (i.e., 100% healed), 2) <100% to 75% healed, 3) 74% to 50% healed, 4) 49% to 0% healed, 5) unable to determine, or 6) not assessed. The IGA score is used to provide a snapshot of overall disease severity in dermatologic clinical studies, (Langley, et al., 2015) including EB (Tabolli, et al., 2009). Results to date in a Phase 1/2a keratinocyte graft study suggest that wound measurements from imaging and IGA score are supportive and well correlated (Dutt-Singkh, et al., 2018).

### **7.4 Patient-Reported Outcome Measures**

A PRO instrument will be used to evaluate secondary endpoints of change in pain and severity at individual wound areas treated with KB103 compared to intra-subject placebo wound areas. At each time point, subjects will be instructed to rate pain symptoms within the last 24 hours for each wound area. Subject global impression of change will be assessed at baseline, and at Days 15, 30, 45, 60 (for adults only), and 90 and unscheduled visits. All study personnel will be trained to on how to administer PROs.

The PRO instrument will be paper-based and collected in person by the treating EB or Principal Investigator. If the EB physician or the Principal Investigator administer the PROs, they will not be able to perform the IGA.

### **7.5 Voice Memo Qualitative Data**

Assistive technology is of utility in the RDEB patient population due to the debilitating nature of the disease. During this study, voice memos will be used to capture qualitative data. Throughout the study subjects and caretakers will be encouraged to record voice memos while at home in between the site visits.

Patients and caretakers are encouraged to record:

- Wound observations, positive and negative
- Questions that they want to ask their doctor at their next visit
- Observations about at-home procedures, including imaging and at-home KB103 administration (if applicable)

Adverse events should be reported immediately by phone as stated in the Adverse Event section below.

Recordings will be downloaded and transcribed for inclusion in the source documentation.

## 8 Safety Assessments

Timing of safety assessments must be performed per the Schedule of Events. Safety assessments include evaluation of medical and medication history, physical / skin examination, vital signs, AEs, and laboratory evaluations. AEs are captured between visits through verbal communication with the site staff. Post-administration changes in these assessments that are deemed to be clinically significant by an Investigator or Sub-Investigator are assessed as AEs.

### 8.1 Viral Shedding

Viral shedding will be analyzed through the collection of blood, urine and skin swabs at a wound areas administered KB103. Swabs will be collected per the schedule of events.

### 8.2 Medical and Medication History

The Investigator or delegated staff performs a complete medical history at Screening, including a medication history. The Investigator or staff must record all clinically or medically relevant information. Medical and medication history are reviewed and updated at baseline. The medical history includes respiratory, cardiovascular, renal, gastrointestinal, hepatic, endocrine, hematological, neurological, psychiatric and other diseases.

### 8.3 Physical / Skin Examination

A qualified individual performs a full physical examination. Body systems evaluated include:

- General appearance	- Skin
- HEENT (Head, Ears, Eyes, Nose, Throat)	- Spine/Neck/Thyroid
- Respiratory	- Cardiovascular
- Abdomen	- Nervous System
- Musculoskeletal	

Abnormalities or changes in severity noted during the exam should be reported in the source document and in the eCRF. If a new clinically relevant finding occurs (not noted prior to KB103 administration), an adverse event form must be completed. In addition, resolution of any abnormal findings during the study are noted in the source document and appropriate CRF if clinically significant. If at any point in the study a skin cancer occurs in the region of the KB103 administration, attempts are made to collect samples of the skin cancer to evaluate cells for the presence of viral vector.

### 8.4 Vital Signs

Vital sign measurements include systolic and diastolic blood pressure, pulse, and respiratory rate as well as temperature. Blood pressure, pulse, and respiratory rate are taken after subjects are

in a rested state. Blood pressure determined by cuff (manual or automated) is acceptable although the same method should be used throughout the study. Temperature, oral or tympanic, is acceptable although the same method should be used throughout the study.

## 8.5 Laboratory Evaluations

### 8.5.1 Serum Chemistry and Hematology

The amount of blood collected should be minimized. Reference ranges are used to assess the laboratory data for clinical significance. Abnormal laboratory values which are unexpected or not explained by the subject's clinical condition should be repeated as feasible until confirmed, explained or resolved. Changes from baseline are recorded as an AE if deemed clinically relevant by the Investigator or qualified designee. The following evaluations are conducted:

#### Serum Chemistry / Metabolic Panel

- Albumin	- AST (SGOT)	- Bilirubin, direct & indirect	- Globulin
- Alkaline Phosphatase Total	- Urea Nitrogen	- CO 2	- Potassium
- Anion Gap	- Calcium	- Creatinine	- Sodium
- ALT (SGPT)	- Chloride	- Glucose	- Total Bilirubin
			- Total Protein

#### Hematology / Complete Blood Count with Differential

- WBC	- Platelet Count	- MCHC	- Monocytes, % and abs
- Hemoglobin	- MCV RDW	- Neutrophils, % and abs	- Eosinophils, % and abs
- Hematocrit	- RBC MCH	- Lymphocytes, % and abs	- Basophils, % and abs

### 8.5.2 Urine Pregnancy Test

A urine pregnancy test is performed at baseline for women of childbearing potential.

### 8.5.3 HSV Antibody Assay

Collect serum at baseline and Day 30 for the purpose of conducting an HSV antibody assay.

### 8.5.4 Collagen VII Antibody Assay

Collect serum at baseline and Day 30 for the purpose of conducting a collagen VII antibody assay. Using the subject's serum, COL7 antibodies are assayed by linear BMZ staining for IgM, IgG, IgA or serum IgG antibodies binding to the epithelium of monkey esophagus with a basement membrane or superficial dermal pattern by indirect immunofluorescence (IIF) microscopy. A non-CLIA western blot assay is also used to assay for COL7 antibodies as a confirmatory assay.

## 9 Adverse Events

Throughout the course of the study (from the date of informed consent), all adverse events (AEs) will be monitored and reported on the AE case report form. If an adverse event occurs, the first concern will be the safety of the study participants. All AEs occurring after administration will be followed throughout the study. All AEs related to study treatments or procedures will be followed until resolved or stabilized or until follow-up is no longer possible.

In general, even when not participating in a clinical trial, the study subjects and their caretakers communicate with their EB doctor on a regular basis via phone. Study subjects and their caretakers will be instructed to report via phone any adverse events that occur during the study while off-site. The events will then be transcribed to the AE CRF.

### 9.1 Definitions

#### 9.1.1 Adverse Events

An Adverse Event (AE) is any untoward medical occurrence in a clinical investigation subject administered a pharmaceutical product and which does not necessarily have a causal relationship with this treatment. An AE can therefore be any unfavorable and unintended sign (including an abnormal laboratory finding), symptom, disease or exacerbation of a pre-existing condition temporally associated with the use of a medicinal (investigational) product.

Subjects should be asked a non-leading question in order to avoid bias in eliciting AEs; such as "How are you feeling?" It is important to question the subject in a non-leading way about changes in their health or concomitant medication usage since their last visit. Where possible, a diagnosis rather than a list of symptoms should be recorded. If a diagnosis has not been made then each symptom should be listed individually.

Each AE requires a complete description including date of onset and corrective actions taken. The intensity of the AE and its relationship to the investigational product, as well as its outcome, must be recorded in the CRF.

Symptoms of the disease under study/lack of efficacy should not be considered as AEs, as long as they are within the normal day-to-day fluctuation or expected progression of the disease. However, significant worsening of the symptoms should be recorded as an AE.

A change in the value of a safety laboratory evaluation can represent an AE if the change is clinically relevant (as determined by the Investigator) or if, during treatment with the investigational product, a shift of a parameter is observed from a normal value to a pathological value, or a further worsening of an already pathological value. When evaluating such changes, the extent of deviation from the reference range, the duration until return to the reference range, either while continuing treatment or after the end of treatment with the investigational product, and the range of variation of the respective parameter within its reference range, should be taken into consideration. The Investigator should decide, based on the above criteria and the clinical condition of a subject, whether a change in a laboratory parameter represents an AE. For

pathological laboratory values that were not present at baseline, follow-up laboratory evaluations should be performed until the values return to within reference range or until a plausible explanation is found.

AEs should be recorded, starting from subject enrollment (date of signature on informed consent) per the Schedule of Events, until the end of the Long-Term Follow-Up Period, and are to be recorded on the appropriate AE pages in the CRF and in source documents. Where possible, all AEs should be followed to resolution, or an outcome is reached. Medical tests and examinations are performed, as appropriate, to document resolution of event(s).

### **9.1.2      Serious Adverse Events**

A Serious Adverse Event (SAE) is any untoward medical occurrence (whether considered to be related to investigational product or not) that at any dose:

- Is fatal.
- Is life-threatening (places the subject at immediate risk of death)
- Requires inpatient hospitalization or prolongation of existing hospitalization.
- Is a persistent or significant disability/incapacity, or
- Is a congenital abnormality/birth defect.

A hospitalization meeting the regulatory requirement for the “serious” criteria is any inpatient hospital admission that includes a minimum of an overnight stay in a health care facility.

Any event that does not exactly meet this definition yet, in the investigator’s opinion represents a significant hazard can be assigned the “other significant hazard” regulatory reporting serious criteria.

Additionally, important medical events that may not be immediately life threatening or result in death or hospitalization but that may jeopardize the subject or require intervention to prevent one of the outcomes listed above, or result in urgent investigation, may be considered serious. Examples include allergic bronchospasm, convulsions, and blood dyscrasias.

SAEs are collected and reported throughout the study duration beginning with enrollment through the end of the Long-Term Follow-Up period. If early termination of study treatment occurs, SAEs continue to be collected until the event resolves.

### **9.1.3      Immune Response Adverse Events**

Observation of a severe immune response determined by the Investigator to be possibly, probably or definitely related to investigational product or a procedure is a stopping criterion.

## **9.2      Severity**

Definitions for classification of severity appear below. The Investigator will review these definitions with the Subject. The Investigator will determine the severity classification based on these definitions, his/her clinical experience with DEB patients, and/or the Subject’s description of the event.

[Note: A “severe” AE is not the same as an “SAE” (serious adverse event), which is defined above.]

**Mild:** Symptoms are barely noticeable or do not make the Subject uncomfortable. The AE does not influence performance or functioning. Prescription drugs are not ordinarily needed for relief of symptom(s).

**Moderate:** Symptoms are of sufficient severity to make the Subject uncomfortable. Performance of daily activities is influenced. Treatment of symptom(s) with prescription drugs or therapies may be needed.

**Severe:** Symptoms are of sufficient severity to cause the Subject severe discomfort. Performance of daily activities is compromised. Treatment for symptom(s) with prescription drugs or therapies may be needed.

## 9.3 Relationship

The Investigator will determine whether the Subject’s symptom or problem is most likely unrelated to the study treatment or is possibly/probably related to the anesthesia employed, the study device, or the injection procedure.

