**Table 1 - KB103-001 Stopping Criteria**

Event	Severity	Number of Events
A treatment emergent serious adverse event that is definitely or suspected to be related to KB103.	Any	1
An AE associated with HSV infection in combination with a positive RCV qPCR assay result.	Any	1
An immune response determined by the Investigator to be possibly, probably or definitely related to investigational product or a procedure.	Severe	1
Any treatment emergent systemic infection designated as possibly, probably or definitely related to investigational product or a procedure.	Moderate or higher	2 or more
A treatment emergent uncontrolled bacterial, viral, or fungal infection in an area administered investigational product where product sterility testing results reported post injection were positive for contamination.	Mild or higher	1

For subject safety, subjects should be followed in accordance with the study visits and procedures as outlined in the protocol. An occurrence of any of these safety observations is shared with the SMC and the appropriate authorities. The SMC reviews the results of the safety investigation and may request any additional data needed to assess the safety of restarting product administration. The SMC determines if the suspension can be lifted or if the trial terminates based on their review of the safety investigation.

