## 9.4 Reporting Procedures

All adverse events occurring after KB103 administration observed by the investigator or reported by the subject (whether or not attributed to investigational product), are reported on the case report form.

Medically significant adverse events considered related to the investigational product by the investigator or the sponsor are followed until resolved or considered stable. The investigator must assign the following attributes: description; dates of onset and resolution; severity; assessment of relatedness to investigational product, and action taken. The investigator may be asked to provide follow-up information.

All deaths occurring on study must be reported to Krystal. These include deaths during the Long-Term Follow-Up period. For all deaths, available autopsy reports and relevant medical reports may be requested.

The investigator should notify the IRB of serious adverse events occurring at the site and other adverse event reports received from the sponsor, in accordance with local procedures.

It is left to the investigator’s clinical judgment whether or not an adverse event is of sufficient severity to require the subject’s removal from study. A subject may also voluntarily withdraw from study due to what he or she perceives as an intolerable adverse event. If either of these occurs, the subject is asked to undergo an early termination assessment and be given appropriate care under medical supervision until symptoms cease or the condition becomes stable. If the subject was permanently withdrawn from the study due to a serious adverse event, this information must be included in either the initial or follow-up Serious Adverse Event Report Form, and in the End of Study Case Report Form.

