**9.4.2 SAE Reporting Procedures**

All Serious Adverse Events (SAEs) that occur after the time of informed consent must be reported to Krystal and the IRB. All subjects with an SAE must be followed and the outcomes reported. The Investigator should supply the Sponsor and the IRB with any additional requested information (e.g., hospital discharge summary, autopsy reports and terminal medical reports). The Sponsor shall evaluate all SAEs and determine if they meet FDA reporting requirements. In the event of an SAE, the Investigator must:

1. Notify Krystal within 24 hours of the Investigator's awareness of the event.
2. Obtain and maintain all pertinent medical records, information, and medical judgments from colleagues who assisted in the treatment and follow-up of the subject.
3. Provide Krystal with a complete, written case history, including copies of supporting reports (e.g., progress notes, laboratory reports) and a statement from the Investigator as to whether or not the event was related to the use of the investigational product.
4. Promptly inform the governing IRB of the event, if it is related. For other SAEs, notify the governing IRB as required by the IRB, local regulations, and the governing health authorities.

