The number and percentage of subjects reporting a TEAE in each treatment group will be tabulated by system organ class and preferred term; by system organ class, preferred term, and severity (mild, moderate, and severe); and by system organ class, preferred term, and relationship (unrelated or related to test article). The incidence of TEAEs will be summarized by preferred term, sorted by decreasing frequency in the KB103 group, for all TEAEs, related TEAEs, serious TEAEs, and TEAEs leading to study drug discontinuation. The number and percentage of subjects reporting a TEAE of wound site reaction (based on the MedDRA higher level term) will be tabulated by treatment group, preferred term and severity (mild, moderate, and severe). The incidence of serious TEAEs, and TEAEs leading to premature discontinuation of treatment by system organ class and preferred term. For all analyses of TEAEs, if the same AE (based on preferred term) is reported for the same subject more than once, the AE is counted only once for that preferred term and at the highest severity and strongest relationship to test article.

In addition, all AEs (including non-TEAEs), serious TEAEs, TEAEs leading to discontinuation of test article, and TEAEs leading to dose interruption of test article will be provided in listings by treatment group, study site, subject, verbatim term, MedDRA system organ class and preferred term, start and end date, seriousness flag, severity, relationship to test article, relationship to study protocol, action taken with test article, non-test article action taken and outcome.

Immune response adverse events due to a severe immune response determined by the Investigator to be possibly, probably or definitely related to KB103 will be summarized by the number and percentage reporting such AEs along with a subject listing.

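### The causality rule in protocol section 9.3 has no category for KB103 and contradicts the sections, stopping criteria and safety tables that need one

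*Protocol*

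**What the plan says.** Protocol section 9.3 is the only section that sets out how the investigator is to judge relationship. The event is either "most likely unrelated to the study treatment or is possibly/probably related to the anesthesia employed, the study device, or the injection procedure".

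Three other protocol sections require a judgement about the product itself:

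- Section 9.1.1, for every adverse event: "The intensity of the AE and its relationship to the investigational product, as well as its outcome, must be recorded in the CRF".
- Section 9.4, in the list of attributes the investigator must assign: "assessment of relatedness to investigational product, and action taken".
- Section 9.4.2, for every serious adverse event: "a statement from the Investigator as to whether or not the event was related to the use of the investigational product".

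None of the three gives categories or definitions.

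The judgement is then used in several places. The first row of Table 1 is triggered by a serious event that is "definitely or suspected to be related to KB103". Its third and fourth rows, and section 9.1.3, use a three-level grade (possibly, probably, definitely) for either the product or a procedure. Protocol section 10.6.1 tabulates events by relationship to KB103. SAP section 9.1 counts drug-related TEAEs and drug-related SAEs, splits events into unrelated and related to test article, and summarises severe immune-response events judged "possibly, probably or definitely related to KB103".

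**The concern.** The one section that tells the investigator how to judge causality leaves out the cause of main interest. An event attributed to the gel, active or placebo, has no place in section 9.3. Two of the three causes it does name, a device and an injection, are not part of treatment in this version, which applies a topical gel. Anaesthesia still fits, because the optional biopsies may need it.

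The judgement feeds a suspension rule, the drug-related safety tables, the follow-up of related events in section 9.4 and prompt notification of the IRB in section 9.4.2. If investigators meet conflicting instructions, the same event could be coded differently from one occasion to the next. The study is small: the protocol allows up to 14 subjects and the SAP counts 12. One subject moving between related and unrelated therefore shifts a reported incidence by 1/12 = 8.3 or 1/14 = 7.1 percentage points.

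**Working it through.** The plan states no figure on this point, so the check sets what section 9.3 can produce against what each user of causality needs.

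**Step 1. Possible outputs of section 9.3.** Unrelated to treatment; or possibly/probably related to anaesthesia, device or injection. There is no output of related to product at any level, and no *definitely* for any cause.

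**Step 2. Table 1, row by row.**

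| Row | Causality needed | Supplied by section 9.3 alone? |
|---|---|---|
| 1. Serious event | Related to KB103; definite or suspected | No |
| 2. HSV-associated event | None: rests on a positive RCV assay ("An AE associated with HSV infection in combination with a positive RCV qPCR assay result") | Not needed |
| 3. Immune response | Product or procedure; three levels | Procedure limb only |
| 4. Systemic infection | Product or procedure; three levels | Procedure limb only |
| 5. Infection at an administered area | None: rests on the sterility result | Not needed |

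Three of the five rows (1, 3 and 4) use a causality grade. Of those three, one is wholly out of reach of section 9.3, and two lose the product limb but keep a procedure limb. The missing *definitely* level does not by itself block rows 3 and 4, since *possibly* and *probably* also qualify there.

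**Step 3. Safety tables.**

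| Output | Needs | Section 9.3 alone gives |
|---|---|---|
| Protocol 10.6.1 tabulation | Relationship to KB103 | Only *unrelated* |
| SAP 9.1 drug-related TEAEs and SAEs | Related to drug | Only *unrelated* |
| SAP 9.1 table by relationship | Unrelated or related to test article | Only *unrelated* |
| SAP 9.1 immune-response summary | Three levels, KB103 only | Nothing that qualifies |
| SAP 9.1 listings | One field for test article, another for study protocol | One mixed item |

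SAP 9.1 also counts a repeated event once, at its strongest relationship to test article. That presupposes an ordered scale for the test article, which section 9.3 does not provide.

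**Step 4. Vocabularies.** Four are in use:

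1. possibly/probably (section 9.3);
2. definitely or suspected (Table 1, row 1);
3. possibly, probably or definitely (Table 1, rows 3 and 4; section 9.1.3; the SAP immune-response summary);
4. unrelated or related (SAP 9.1 tables).

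Nothing says whether *possibly* counts as *related* in the SAP tables, or which grades amount to *suspected* in row 1. SAP section 6.3 says causality may not be missing and will be queried, but a query cannot settle which scale applies.

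**The case against.** The best defence is that the plan asks for the right data elsewhere. Sections 9.1.1 and 9.4 make product relatedness mandatory for each event, and section 9.4.2 requires a written statement for every serious event, which is close to what the first row of Table 1 uses. Table 1 and section 9.1.3 name their own levels and do not refer back to section 9.3. The opening of section 9.3 does mention study treatment, so treatment causality is at least raised. Protocol section 1.6 reports no KB103-related events under version 2, so relatedness to KB103 was being judged in this study, although the text of section 9.3 in that version is not available.

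Much of this stands, and it limits the point. A reader might infer that the stopping criteria and the drug-related tables cannot be fed at all, or that three of the five stopping rows are disabled. The documents do not support that. Rows 2 and 5 need no causality grade, rows 3 and 4 accept a procedure as well as the product, and even row 1 is out of reach only if section 9.3 is followed in isolation from the mandatory items in 9.1.1, 9.4 and 9.4.2. Nor can it be said that a product-related signal was or will be missed: the case report form is not among the documents.

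The defence does not cure the defect. The sections that require product relatedness give no scale. Table 1 and section 9.1.3 name levels without defining them or agreeing on one set. No text connects any of them to the related/unrelated split in the SAP.

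**Conclusion.** The point holds as an internal contradiction about a safety variable. Section 9.3 conflicts with protocol sections 9.1.1, 9.1.3, 9.4, 9.4.2 and 10.6.1, with Table 1 and with SAP section 9.1, and no single causality scale or mapping exists. This is more than missing detail: for a topical product, a stated rule lists the wrong causes. Its size, reading section 9.3 alone, is one stopping row without any input, two more without their product limb, and drug-related tables that could contain only *unrelated*. Read with the rest of the protocol, the judgement is requested but its scale is undefined.

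The conclusion rests on the text only. If the AE form already carries a separate, graded item for the product, the practical effect shrinks to the unmapped vocabularies. It should be corrected, because the input to a suspension rule ought not to depend on which section the investigator happens to read.

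**What to change.** - Replace section 9.3 so that each adverse event is graded for relationship to the investigational product (KB103 or placebo gel) and, as a separate item, to a study procedure. Use one ordered scale that includes unrelated, possibly, probably and definitely. The last three are already in Table 1 rows 3 and 4; *unrelated* has to be added, since Table 1 does not contain it.
- Reconcile that scale with row 1 of Table 1, which reads "A treatment emergent serious adverse event that is definitely or suspected to be related to KB103". Which grades meet that row is for the sponsor and the Safety Monitoring Committee to state; the documents need to give one answer.
- State in SAP section 9.1 which levels count as related to test article, and apply that mapping to events from all protocol versions the SAP pools. Fix it before the final safety tables are run, since the SAP was written after a partial analysis of an unblinded study.
- Check that the AE form matches. If it used other categories, document how they convert.

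The cost is one replaced protocol paragraph, a reconciliation of Table 1's row 1 wording, a mapping sentence in the SAP and a check of the form. No dose, threshold or schedule is affected.
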